#### Cardiovascular assessments

The following anthropomorphic assessment will be performed for all patients at baseline and at the end of the study. Anthropomorphic measurements include body heights, body weight, waist and hip circumferences, two consecutive blood pressure (BP) readings in sitting position and heart rate. Hypertension status is defined as systolic blood pressure (SBP)  $\geq 140$  mmHg or diastolic blood pressure (DBP)  $\geq 90$  mmHg or the use of antihypertensive agents. Other data collected at baseline include menopausal status, smoking and drinking habits, social economic status, history of diabetes, hypertension, hypercholesterolemia, dyslipidemia, overt CVD and cerebrovascular diseases, peptic ulcer disease and family history of CVD, diabetes and cerebrovascular diseases in first-degree male relatives  $< 55$  years of age or first-degree female relatives  $< 65$  years of age. Drug history is retrieved from case notes or elicited during the clinical assessment. Body weight and blood pressure will also be measured during each visit to the rheumatologist.

Laboratory assessment at baseline include fasting blood glucose, fasting lipid profile (total cholesterol [TC], low-density lipoprotein-cholesterol [LDL-C], high-density lipoprotein-cholesterol [HDL-C], triglycerides [TG]), fibrinogen, thyroid function test, creatinine kinase and uric acid. Fasting sugar and lipid profile will also be measured at 6 and 12 months. Hemoglobin A1c levels will be measured at baseline and 12 months for patients with known diabetes.

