#### Use of statins

Group 1 patients will be prescribed statin when FRS > 10%; while group patients will be prescribed statin upon presence of carotid plaque as reported from carotid ultrasound. The decision will solely be made base on the randomized group by either FRS>10% or presence of carotid plaque.

We choose atorvastatin 20 mg daily since generic atorvastatin is available in the Hong Kong Hospital Authority drug formulary. Each tablet cost HK \$ 0.28 and the yearly cost is HK \$ 102.2 (around US \$ 13) per person. Atorvastatin 20 mg is recommended as the preferred initial high-intensity statin to use because it is clinically and cost effective for the primary prevention of CVD according to the national institute for Health and Care Excellence (NICE) guideline from the United Kingdom. Nonetheless, similar data is lacking in Hong Kong.

No trials to date that have evaluated effects on CVD events have tested any medication in combination with statins or treatment to specific LDL-C goals, therefore we do not intensify the regimen for any particular level of LDL-C response. Measuring LDL-C response after initiating therapy in this study is mainly to assess adherence. In this primary prevention trial, in patients who do not tolerate statins, no lipid-lowering therapy will be administered. Potential interventions include lifestyle modification and, in higher-risk patients, antiplatelet therapy.

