### **Outcome measures**

The primary outcome is the change in FRS. Although this algorithm was developed for prediction of absolute coronary risk among patients without clinical manifestations of CAD, they combine the following major risk factors recognized for coronary and other atherosclerotic CVD (ASCVD): age, sex, high BP, smoking, dyslipidemia, and diabetes status. We use risk scores as a composite measure of change in modifiable major risk factors, rather than as a predictor of risk. This approach has been previously used in evaluating effects of nurse- and dietitian-led case management program to reduce CV risk (30). Baseline age will be applied when calculating the FRS at 12 months.

Secondary end points included

- 1) Change in arterial stiffness in subjects
- 2) Change in individual modifiable risk factors (systolic and diastolic BP; TC, LDL-C, HDL-C and TG levels; TC/HDL ratio; and hemoglobin A1c value in patients with diabetes)
- 3) The number of measures taken against comorbidities.
- 4) Proportions of patients achieving remission.
- 5) Changes in IMT and proportion of plaque progression in subjects between 2 groups

The trial will be conducted with compliance to ICH-GCP and Declaration of Helsinki.

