**Statistical analysis:**

Descriptive statistics will be used for demographic and clinical variables included frequencies, percentage, means and standard deviations, median and interquartile range. Comparisons in demographic and clinical characteristics at baseline will be performed using chi-square test, independent samples *t*-test or Mann-Whitney *U* test, depending on distribution of data. We will compare the proportion of participants eligible for statin treatment using FRS >10% vs carotid ultrasound criteria using the McNemar test. The intervention effect on the primary and secondary outcomes will be examined at 12 months on an intention-to-treat basis using a mixed-effects regression model adjusted for baseline FRS. The model will also take into account random effects associated with physicians and clinics in a hierarchical structure. The magnitudes and patterns of missing data will be examined by the randomized group. Missing outcomes at the 12-month follow-up will be imputed using the method of the baseline observation carried forward. The same mixed-effects model will be used for subgroup analyses defined by sex and underlying diseases. All statistical analyses will be conducted using IBM SPSS Statistics Version 23 (IBM, Armonk, NY, USA). A level of significance of *p* =0.05 is used.

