**Sample size calculation:**

The sample size is estimated by the Power Analysis and Sample Size for Windows software (PASS 2000, NCSS, Utah, USA). All calculations will use a two-sided  $\alpha$  of 0.05 and  $\beta=0.2$  achieving 80% power. From our previous cohort study, standard deviation of FRS was 8. Taking population variance of FRS as 64, and suppose 4 unit drop in FRS is clinically meaningful. A sample size of 63 is required in each group. Assuming a drop-off rate of 10%, a total sample size of 140 (i.e. 70 per arm) would be sufficient.

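### Baseline carried forward as the only stated handling of missing 12-month outcomes scores each dropout as zero FRS change and ignores interim data; the harm is modest and the remedy cheap

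*Protocol*

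**What the plan says.** All references are to the protocol.

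- **Outcome measures:** "The primary outcome is the change in FRS", and "Baseline age will be applied when calculating the FRS at 12 months".
- **Statistical analysis:** effects on the primary and secondary outcomes "will be examined at 12 months on an intention-to-treat basis using a mixed-effects regression model adjusted for baseline FRS", with random effects for physicians and clinics. On missing data: "Missing outcomes at the 12-month follow-up will be imputed using the method of the baseline observation carried forward". The only other step is to look at the extent and pattern of missingness by arm.
- **Cardiovascular assessments:** "Fasting sugar and lipid profile will also be measured at 6 and 12 months", and "Body weight and blood pressure will also be measured during each visit to the rheumatologist".
- **Sample size calculation:** 63 per group, then "Assuming a drop-off rate of 10%, a total sample size of 140 (i.e. 70 per arm) would be sufficient".
- **Use of statins:** "in patients who do not tolerate statins, no lipid-lowering therapy will be administered".

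**The concern.** Age is held at its baseline value, so a carried-forward FRS gives a change of exactly zero. The model treats that zero as if it had been observed. This is a single untestable assumption, applied to every dropout whatever was measured before the patient left. A patient whose lipids fell at 6 months and who then missed month 12 is scored as unchanged.

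Two things are at stake. If dropouts would have changed as completers do, the estimated difference shrinks. If both arms improve, the size and even the sign of the error depend on how dropout is spread between arms. Improvement in both arms is plausible, because both receive the nurse-led programme, rule-based statin prescribing and protocolised treatment of the arthritis. The usual defence that carrying baseline forward is conservative is therefore not safe here.

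**Working it through.** **1. The plan's own figure.** Inputs from Sample size calculation: SD 8, difference 4, two-sided α 0.05, power 80%. n per arm = 2 × (1.960 + 0.842)² × 64 / 16 = 62.8, so 63. Then 63 / 0.9 = 70 per arm and 140 in total. The figure reproduces, with 80.1% power at 63 completers per arm. Ten per cent of 70 is 7 dropouts per arm.

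**2. Attenuation with equal dropout unrelated to response.** If dropouts would have changed as completers do, the expected contrast is (1 − 0.10) × 4.0 = 3.6. A large baseline-adjusted simulation gave 3.59 with baseline carried forward and 3.99 in completers.

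**3. Power.** The imputed zeros also shrink the variance. Per arm, the variance of change is (1 − d) × 64 + d(1 − d) × m², where d = 0.10 and m is the mean change. With 70 per arm and a contrast of 3.6:

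| Mean changes (assumed) | Sum of the two variances | SE | Power |
|---|---|---|---|
| 0 and −4 | 116.64 | 1.291 | 79.6% |
| −2 and −6 | 118.80 | 1.303 | 78.9% |
| −4 and −8 | 122.40 | 1.322 | 77.7% |

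Against 80.1%, the loss is 0.5 to 2.4 points.

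**4. Comparison with multiple imputation.** The simulation used 70 per arm, SD 8, equal 10% dropout at random, a common fall of 2 and an effect of 4. The baseline-to-12-month correlation r was assumed, as was one 6-month proxy correlated 0.6, 0.75 or 0.85 with FRS. Physician and clinic effects were not modelled.

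| r | Power: carried forward | Power: imputation | RMSE: carried forward | RMSE: imputation |
|---|---|---|---|---|
| 0.5 | 86.8–87.7% | 88.3–88.8% | 1.21–1.26 | 1.23–1.27 |
| 0.65 | 94.1–94.2% | 95.2–95.8% | 1.07–1.08 | 1.06–1.07 |
| 0.8 | 99.3–99.4% | 99.6–99.7% | 0.89–0.91 | 0.84–0.86 |

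Under a null effect with equal dropout at random and a common fall of 4, type I error was 4.9–5.0% with baseline carried forward and 4.6–5.0% with imputation.

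**5. If dropouts lose part of the change.** Let L be the share of the completer change that dropouts lose, at 10% dropout in each arm.

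- Truth = 4(1 − 0.1L).
- Error with baseline carried forward = 3.6 − truth = −0.4(1 − L).
- Error under missing at random, with nothing visible in interim data = 4.0 − truth = +0.4L.
- The errors are equal in size at L = 0.5, where truth is 3.8 and each method is off by 0.2.

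At L = 1 the truth is 3.6 and baseline carried forward is exact. Imputation then gave 3.76–3.82 if the return was visible at month 6 in all dropouts, 3.88–3.92 if only half had month-6 data, and 4.0 if it was not visible.

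**6. Unequal dropout (assumed 5% and 15%), dropouts changing as completers do.**

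- No true effect: false contrast = common fall × dropout difference. This is 2 × 0.10 = 0.2 or 4 × 0.10 = 0.4. Simulated type I error was 5.3–5.8% and 6.1–8.2% respectively, against 4.4–4.6% with imputation.
- True effect 4.0, changes −4 and −8: 0.85 × 8 − 0.95 × 4 = 3.0, or with the dropout rates swapped 0.95 × 8 − 0.85 × 4 = 4.2. The error can go either way.

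**7. Response-dependent dropout (assumed).** Here there was no true effect, 10% dropout in both arms, a common fall of 2, and dropout in one arm tied to 6-month change. Baseline carried forward gave a false contrast of 0.23–0.39 and type I error of 5.9–6.6%. Imputation gave 0.00–0.01 if all dropouts had month-6 data and 0.10–0.14 if half did, with type I error of 4.5–5.3%.

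**The case against.** The strongest reply is that this exchanges one untestable assumption for another. Nothing in the protocol places L above or below one half, and the rule for patients who do not tolerate statins makes some return to baseline plausible. Under full return, imputation was further from the truth than baseline carried forward in every variant simulated. Even where dropouts change as completers do, RMSE is about equal at r = 0.5 and 0.65, and baseline carried forward is only about 5–6% worse at r = 0.8. The bias of 0.4 is 0.05 SD. All of this stands, and it keeps the point modest.

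It is also true that patients who leave before month 6 have no 6-month laboratory values, that the protocol does not say when dropout is expected, and that the proxy correlations above are assumed. The gain from interim data is therefore uncertain in size. The planned look at missingness by arm would reveal unequal dropout, but it would not correct the estimate.

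What the reply does not restore is the claim that the rule is safely conservative, or a reason to leave FRS components already collected out of the handling of missing values.

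A reader might infer that the trial is underpowered or that its allowance for dropout is wrong. Neither follows: 63/0.9 = 70 is correct and the power loss is about 2 points at most.

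**Conclusion.** The point holds as a modest one that is worth changing. With 10% dropout, equal by arm and unrelated to response, 4.0 becomes 3.6 if dropouts would have changed as completers do. Type I error then stays near 5%, and overall error is similar to that of multiple imputation except at a high baseline-to-12-month correlation.

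A reader might go further and infer that the rule inflates type I error in this trial. The documents do not support that. The false contrasts need both arms to improve, and dropout to differ by arm or depend on response. The protocol gives no figure for any of these, so they show only that the rule is not reliably conservative. Nor can one say that imputation is always closer to the truth: if dropouts lose more than half of the change and interim data do not show it, baseline carried forward is closer.

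The conclusion rests on the protocol's SD, effect and dropout rate, and on simulations without physician and clinic effects. It concerns the stated method only. A statistical analysis plan, not seen here, may add sensitivity analyses.

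**What to change.** Replace the missing-data sentence in Statistical analysis so that the primary analysis:

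- multiply imputes 12-month FRS separately by arm, using baseline values, 6-month lipids and glucose, and visit blood pressure;
- includes physician and clinic in the imputation model where numbers allow;
- fits the stated baseline-adjusted mixed model to all randomised patients in each completed data set and pools the results;
- keeps baseline carried forward as a sensitivity analysis.

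Do not construct a 6-month FRS, because smoking status is not scheduled at 6 months. Fitting the model only to observed 12-month outcomes is a weaker fallback. With one post-baseline FRS it amounts to a complete-case analysis, ignores the same interim data, and drops randomised patients from an analysis described as intention-to-treat.

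The cost is a short change of text and modest extra analysis, with no new data and no change in sample size. The downside is that the primary result then relies on missing at random. It could overstate the effect by up to 0.4 units at 10% dropout if dropouts return fully to baseline and interim data do not show it. The retained sensitivity analysis shows that bound.

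### The subgroup sentence reuses a model with no arm-by-subgroup term; read naturally, it means separate fits in each stratum, which cannot show whether effects differ by sex or disease

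*Protocol*

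**What the plan says.** One sentence in the protocol's Statistical analysis section covers subgroups: "The same mixed-effects model will be used for subgroup analyses defined by sex and underlying diseases".

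The model meant is described just before it. Outcomes at 12 months are examined by intention to treat "using a mixed-effects regression model adjusted for baseline FRS", and "The model will also take into account random effects associated with physicians and clinics in a hierarchical structure". No subgroup term and no arm-by-subgroup term is listed. The section gives one threshold for everything: "A level of significance of *p* =0.05 is used". It states no separate rule for reading subgroup results.

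The underlying diseases are rheumatoid arthritis (RA) and psoriatic arthritis (PsA). The protocol gives no expected proportions by disease or by sex.

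**The concern.** If the model is reused unchanged, it can yield subgroup results only by being fitted within men, women, RA and PsA in turn. Each fit answers whether there is an effect in that stratum. None answers whether the effect differs between strata, which is the usual reason for looking at subgroups. A significant result in one stratum beside a non-significant one in the other is weak evidence of a difference. The smaller samples alone will often produce that pattern when the effect is the same in everyone.

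In this trial, a reader could be led to think that the ultrasound-based statin rule works in one disease or one sex but not the other, with no evidence of a difference behind it.

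**Working it through.** **Inputs from the protocol (Sample size calculation).** "standard deviation of FRS was 8"; "suppose 4 unit drop in FRS is clinically meaningful"; "All calculations will use a two-sided" alpha of 0.05, "achieving 80% power"; 63 per group, 10% drop-off, 140 in total.

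**Assumptions, not in the protocol.** The larger stratum holds 50% to 80% of patients, with the same split in both arms. Clustering by physician and clinic is ignored. A normal approximation is used, so fractional stratum sizes are kept.

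**1. The protocol's own figure.** n per arm = 2 × [8 × (1.960 + 0.842) / 4]² = 62.8, so 63. Allowing for 10% drop-off, 63 / 0.9 = 70 per arm, or 140 in total. Both stated figures reproduce.

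**2. Power within a stratum when the true effect is 4 units in everyone.** With m patients per arm in the stratum, power = Φ(4 / [8 × √(2/m)] − 1.960). The chance that exactly one of the two strata is significant is p₁(1 − p₂) + p₂(1 − p₁).

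| Split | Patients per arm | Power in each stratum | Exactly one significant |
|---|---|---|---|
| 50:50 | 31.5 / 31.5 | 51% / 51% | 50% |
| 70:30 | 44.1 / 18.9 | 65% / 34% | 55% |
| 80:20 | 50.4 / 12.6 | 71% / 24% | 61% |

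Noncentral-t power gives the same last column to the nearest per cent.

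**3. Allowing for baseline adjustment.** The SD of 8 is that of FRS itself, whereas the model adjusts for baseline FRS. With correlation r between baseline and 12 months, the residual SD is 8 × √(1 − r²). The protocol gives no r. Two assumed values:

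- r = 0.7: residual SD 5.71. Exactly one significant: 33% at 50:50 (power 79% in each), 57% at 80:20 (94% and 42%).
- r = 0.8: residual SD 4.80. Exactly one significant: 16% at 50:50, 45% at 80:20.

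**4. Both factors together.** A simulation of 20,000 trials used 63 per arm, sex and disease each about 50:50 and unrelated, and known SD 8. With a uniform 4-unit effect, sex or disease gave a significant/non-significant split in about 67% of trials. With no effect at all, at least one of the four subgroup tests was significant in about 17% (independent tests would give 1 − 0.95⁴ = 18.5%).

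**5. The interaction test.** Its standard error is 8 × √(2/a + 2/b), where a and b are the per-arm sizes of the two strata.

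- 50:50: standard error 2.85; power for a 4-unit difference in effect 29%; difference detectable with 80% power 2.802 × 2.85 = 8.0 units.
- 80:20: standard error 3.56; power 20%; detectable difference 10.0 units.

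In the simulation the test falsely declared a difference in about 5% of trials, as intended. With r = 0.7 its power would rise to about 50% (50:50) or 35% (80:20).

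**The case against.** The strongest reply is that the fault lies in a reading of the sentence. The protocol does not say that the model is fitted separately in each stratum, and the same type of mixed model with an added interaction term would also fit the wording. A reader might infer that the plan intends to compare subgroup p-values and claim different effects from them. The document does not support that: it states no such rule, and its aim, outcomes and purpose treat RA and PsA together. The exact parameterisation could also be set out in a statistical analysis plan that is not shown.

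Much of this stands. It limits the finding to what the sentence most naturally implies. It does not remove the finding, because the protocol is not silent: it names a method, describes the model without a subgroup term, and calls it the same model.

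The size is also open to challenge, fairly. The 50% to 61% range rests on assumed splits and on the unadjusted SD, and step 3 shows that it falls once baseline adjustment is allowed for. The interaction model is not entirely without drawback either: with low power, a non-significant interaction could be misread as consistency of effect.

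**Conclusion.** The point holds as a minor one. As written, the subgroup method most naturally means separate tests at 0.05 in each stratum, and these cannot show whether effects differ. If the true effect were uniform and as large as planned, one stratum of a pair would be significant and the other not in about 50% to 61% of trials at SD 8, for splits from 50:50 to 80:20. With an assumed baseline correlation of 0.7 the range is about 33% to 57%. The splits and the correlation are assumptions, and clustering is ignored.

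The primary comparison, its type I error and the sample size are not affected.

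**What to change.** Replace the subgroup sentence with text to this effect: for each of sex and underlying disease, fit the primary model in all randomised patients with the subgroup and arm-by-subgroup terms added, one model per factor. Report the interaction estimate and the subgroup estimates from that model, with 95% confidence intervals. Make no claim of differing effects from within-subgroup p-values. Label these analyses exploratory.

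Add one line on the limits: at SD 8, power to detect a 4-unit difference between strata is only about 20% to 29%, so a non-significant interaction does not show that the effects are the same.

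The cost is a sentence or two of text and two extra terms in each subgroup model. Data collection and sample size do not change. The low power is the one drawback to disclose. It is a reason for caution in reading the results, and no reason to prefer separate tests.

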**Sample size calculation:**

The sample size is estimated by the Power Analysis and Sample Size for Windows software (PASS 2000, NCSS, Utah, USA). All calculations will use a two-sided  $\alpha$  of 0.05 and  $\beta=0.2$  achieving 80% power. From our previous cohort study, standard deviation of FRS was 8. Taking population variance of FRS as 64, and suppose 4 unit drop in FRS is clinically meaningful. A sample size of 63 is required in each group. Assuming a drop-off rate of 10%, a total sample size of 140 (i.e. 70 per arm) would be sufficient.

**(G) Purpose and potential for implementation of results**

Elevated CVD risk is a significant public health problem that contributes greatly to the increased morbidity and shortened lifespan of individuals with RA and PsA. Over the past decades, there has been great progress into the understanding of the severity of CVD risk in these patients but these risk factors are not well managed. The development of the high-risk strategy is therefore necessary, with more intensive therapy reserved for patients identified as high-risk, e.g. because they have high-risk FRS. However, these risk scores under-estimated CV risk in patients with RA and PsA. An intermediate approach is to use quantification of preclinical vascular disease to further identify high-risk patients. Results from this study will provide clinical implications in terms of detecting and managing cardiovascular morbidity in patients with RA and PsA.

